3.4.2.3 Review visits and parameters for evaluation of clinical outcomes

The primary purpose of review appointments is to assess healing and continued root development. Patients will be reviewed according to the set protocol stated above. Each tooth will be accounted for as an individual case, regardless of whether it originates from the same patient or not. Data will be recorded into a data collection sheet (**Appendix F**) and transferred into an Excel spreadsheet prior to analysis.

During the review visits, the following outcomes will be assessed:

Clinical-

- Presence/absence of tooth
- Mobility
- Periodontal probing (6 point evaluation for pocket depth)
- Tenderness to percussion and palpation
- Percussion note
- Free from pain or discomfort
- No evidence of labial swelling or abscess, signifying continued presence of infection
- Presence of discolouration

Radiographic

Standardised periapical radiographs will be taken before the start of treatment, at the end of the treatment and then again at each recall visit post treatment. Final outcome measures will be recorded at the 18th month review. This protocol is a standard clinical protocol and no additional radiographs will be taken for the purposes of this study.

A standardized beam aligning holder for both direct and indirect sensors will be utilized during taking of radiographs. All radiographs will be evaluated for periapical status and qualitative and quantitative status of root dimensions.

Standard Pulp Sensibility Tests

At each recall, pulp sensibility responses will be evaluated using thermal test (EndoIce) and Electric Pulp Test (EPT). Evaluation of tooth mobility, tenderness to percussion and palpation will also be carried out. This procedure will be done at the baseline, and during each subsequent review visit following completion of treatment.

Photography

Standardized intra-oral photographs will be taken before the start of the treatment and each recall visit. Post treatment crown colour in comparison to the pre-operative photographs and to that of the contralateral tooth will be assessed using the MathWorks software as described in the study by Day et al

(24). To facilitate comparison between pre-operative and post-treatment photographs and then quantify any color change, a dedicated software developed using MathWorks (Natick, MA) will be used. The software will be used to calculate the red-green-blue (RGB) and L*, a*, b* values for 2 areas of interest, after it had first corrected the color of the second photograph to that of the first. The program will evaluate the values for the reference (baseline) and final review photographs, together with the change in color, CIELAB ΔE .

Patient Reported Outcomes

For each session, the patients will be requested to evaluate their pain scores both pre-operatively (which will be related to the condition) and also post-operatively (related to treatment procedures). They will also be requested to fill in a patient satisfaction report which will evaluate the following outcomes: (1) Perceived improvement in oral health-related quality of life (OHRQL), (2) history of inter-appointment symptoms, and (3) overall patient satisfaction ratings. The questionnaires evaluating patient report outcomes will be piloted prior to use. (**Appendix G**)

3.4.2.4 Radiographic Analysis

Measurements of digital radiographs will be carried out using the measurement tool available in the VixWin digital radiography viewing software. Calibration of the measurements (based on the known width of the digital film) will be done prior to carrying out of quantitative measurements. Digital radiographs will be read in a darkened room, on a standardized monitor (DELL E2213H 1920 x 1080 Pixel Resolution 22" LCD Display) screen and computer with Windows Operating System (OS).

For length measurements, the point of reference will be the cement-enamel junction (CEJ) and Measurement ideals are referenced from the article by Bose *et al*(10), Chugal *et al* 2001(25) and Yu *et al* 2012(26). Below are the set definitions and proposed criteria which will be used for measuring the abovementioned parameters for radiographic analysis:

1. Size of periapical lesion,
 - Measured using the periapical index (PAI) scoring system (27)
2. Resolvement of periapical lesion;
 - Defined as the complete absence of existing periapical radiolucency as compared with pre-operative radiograph
3. Root length

- Quantitative outcome: Measured in millimeters (mm) as a straight line from the CEJ to the radiographic apex of the tooth;
- Binary outcomes: Comparison of increase in root length (Yes/No)
- Both pre and post-operative (measured during the recall visits) will be recorded.

4. Dentinal wall thickness measurements (at apical and mid root)
 - Quantitative outcome: Measured in millimeters (mm) at the apical one third of the tooth;
 - Binary outcomes: Comparison of increase in dentine wall thickness (Yes/No)
 - The dentinal wall thickness for both the preoperative and recall images will be measured at the level of the apical one third of the preoperative root canal length measured from the CEJ. The root canal width and the pulp space will be measured at this level, and the remaining dentin thickness will be calculated by subtracting the pulp space from the root canal width
5. Width of apex;
 - Measured in millimeters (mm) as the distance between the inner sides of the open apex
 - Binary outcomes: Comparison of decrease in width of apex (Yes/No)
6. Continued root development;
 - Measured as Postoperative root length minus Pre-operative root length (in millimeters) (mm); percentage change will also be calculated
7. Closure of apex;
 - Measured by means of visual identification; defined as approximation of the inner sides of the root tips.
8. Pulp canal obliteration
 - Defined as hard tissue deposited along the wall of the root canal which fills most of the pulp canal as detected through comparisons with pre-operative radiographs.

Since this study involves primarily young subjects (i.e. children), to account for possible clinical variations, both binary and quantitative outcomes will be collected. This is to account for clinical variations which may occur during the treatment process. The following parameters will be evaluated:

- Reduction in size or resolution of periapical lesion
- Pulp canal obliteration
- Anomalies detected - any deviation from the norm, e.g. pulp canal obliteration, ingrowth of osteoid (bone)-like tissue etc.
- Continued root development and changes in dentinal root thickness and width of apex will be quantified using VixWin and Image J software.

Two independent assessors will be involved in the clinical and radiographic analysis. Prior to commencement of the analysis, the investigators will undergo training and calibration. All analysis will be carried out separately by the assessors, and results will be compared.

All radiographs will be randomly shown to the examiners who will be asked to score the test parameters. All available radiographs will be evaluated at the same time, and using the same computer under standardized monitor display configuration and lighting conditions. All measurements will be repeated after 1 week, and the mean of the 2 replicates will be considered as the final value. In cases where there is doubt or a large discrepancy between readings, both investigators will discuss and come to an agreement. All patient identifiers will be removed from the radiographs prior to radiographic analysis to prevent potential measurement bias.

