This also begs the question if antibiotics are truly a necessary and beneficial component in the preparation for a sterile root canal. Prior laboratory in-vitro studies have determined that disinfection protocols have a profound effect on stem cells of the apical papilla (SCAP) as well as dentine microhardness. Yassen et al demonstrated that dentine microhardness was significantly reduced when triple or double antibiotic mixtures were used for treatment of dentine compared to Ca(OH)_2 (20). Antibiotic paste formulations used in RET procedures were found to be directly toxic to stem cells even at concentrations as low as 1% of doses currently used in treating patients, while conversely dentin conditioning with Ca(OH)_2 was found to promote SCAP survival and proliferation (21, 22). This may well have clinical implications impacting fracture resistance and SCAP survival in immature permanent teeth with already compromised root thickness.

Given that this procedure (Regenerative Endodontic Therapy using revascularization via blood clotting method) has been carried out in children in Singapore since 2007, and a retrospective study is in progress, it is considered timely to conduct a prospective randomized controlled study to evaluate the need for antibiotic pastes and the outcome and success of RET.

2.0 Research questions/Aims and Objectives:

Research questions:

1. Are there differences between treatment outcomes of a 2-Mix antibiotic paste (Ciprofloxacin and Metronidazole) vs disinfection with the currently accepted multiple-visit protocol in non-surgical root canal treatment (i.e. disinfection with NaOCl solution followed by Ca(OH)₂ as inter-appointment dressing) with respect to:
 - i. Resolution of apical periodontitis.
 - ii. Thickening of dentinal walls and/or continued root development with or without apical closure.
2. Which are the baseline characteristics which could predispose a case to successful outcome?
3. Will discolouration of teeth occur and to what extent?

Primary aim

1. To assess frequency of periapical healing in the two sets of experimental protocols.
2. To study the differences in qualitative and quantitative increase in root dimensions of different protocols, by evaluating continued root development and thickening of dentinal walls.

Secondary aims

1. To evaluate if tooth discolouration occurs by evaluating the changes in tooth colour following treatment using the different protocols.

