3.3 Outcome measures

The study will evaluate the following clinical outcomes following this procedure:

- i. Resolution and healing of periapical radiolucency
- ii. Measurements of thickening of dentinal walls and/or continued root development with or without apical closure
- iii. Discolouration of tooth
- iv. Patient reported outcomes, including oral health-related quality of life (OHRQL), symptoms, and satisfaction ratings.

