3.4. Participants

3.4.1 Inclusion and Exclusion criteria

The inclusion criteria are as follows:

1. Patients aged 6-16 years of age
2. Patients who are fit and healthy or with ASA 1 or ASA 2 medical conditions
3. Patients with cooperation level that would allow treatment under local analgesia, application of rubber dam isolation and taking of intraoral radiographs.
4. Patients with permanent premolars that have incomplete root formation with an open apex of greater than 1mm width as observed radiographically and of single root canal morphology (23)
5. Patients with single rooted immature permanent teeth having one of the following pulpal and periapical diagnosis:
 - a. Pulpal
 - i. Necrotic pulp
 - ii. Symptomatic and inflamed pulp not expected to heal. During attempted Cvek or cervical pulpotomy procedures, if the pulpal bleeding does not stop with direct pressure within 5 minutes, pulpectomy will be carried out and the patient will be recruited for RET procedures.
 - b. Periapical
 - i. Symptomatic apical periodontitis (with or without a radiographic apical lesion)
 - ii. Asymptomatic apical periodontitis (with a radiographic apical lesion)
 - iii. Acute apical abscess
 - iv. Chronic apical abscess

Teeth will be deemed non-vital if either are non-responsive to sensibility tests (i.e. EPT and cold tests), and/or present with signs and symptoms of non-vitality (e.g. swelling and abscess).

The exclusion criteria are as follows:

1. Patients aged > 16 years of age.
2. Patient with known allergies to Ciprofloxacin (or any fluoroquinolones class of antibiotics) or Metronidazole antibiotics.
3. Patients with medical conditions and/or receiving medications that would affect:
 - a. Their body's ability to heal e.g. Diabetes; or
 - b. Their ability to clot efficiently, e.g. Haemophilia
4. Patients with risk of developing infective endocarditis or immune compromised patients.
5. Patients with non-vital permanent premolars where root development is already deemed to be completed (i.e. foramen size of 0-1.0mm diameter as determined radiographically).
6. Impacted or horizontally tilted teeth.
7. Concurrent signs of irreversible pathological root resorption determined radiographically, e.g replacement or internal root resorption, which could otherwise affect the prognosis of the tooth.
8. Uncooperative patients, or those unable to cope with treatment under local anaesthesia, rubber dam isolation and taking of intraoral radiographs.

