4.5. Statistical methods

All analysis will be carried at a tooth level, where each tooth will be accounted for as an individual case. Descriptive statistics (both discrete and non-discrete variables), which will include means, standard deviations, frequencies and percentages will be determined. Data will be checked for homogeneity of variance prior to application of statistical tests. Appropriate correlation and regression analysis will be

employed in consultation with a biostatistician. Inter and intra-operator variability scores will be evaluated using Kappa statistics. The significance level will be set at $p<0.05$. All data will be analyzed using SPSS Statistical Package (IBM SPSS Statistics).

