6.2. Ensuring patient return for reviews

As this is a randomized controlled clinical study, it is possible that patients may not return for recalls following completion of procedures, resulting in drop outs. As such, a 10% margin for drop outs has been assumed in the power calculation. Intention to treat analysis will also be carried out.

Patients enrolled in the study will be followed up closely, and appointments at appropriate intervals as specified in the protocol will be made. Patients will be reminded to attend the review visits 2 days in advance via telephone or SMS. Treatment rendered and review visits will not be charged.

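### Does the periapical healing outcome break down for teeth that enter the trial without a radiographic lesion?

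*Protocol*

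**What the plan says.** Section 2.0 of the protocol sets primary aim 1: "To assess frequency of periapical healing in the two sets of experimental protocols". The matching research question in the same section is worded as "Resolution of apical periodontitis", while section 3.3 lists the outcome as "Resolution and healing of periapical radiolucency".

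Section 3.4.2.4 gives two periapical measures. Item 1, lesion size, is "Measured using the periapical index (PAI) scoring system", with no cut-off between healed and not healed. Item 2, resolution of the lesion, is the only yes/no rule: "Defined as the complete absence of existing periapical radiolucency as compared with pre-operative radiograph".

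Section 3.4.1 lists among the eligible periapical diagnoses: "Symptomatic apical periodontitis (with or without a radiographic apical lesion". A lesion on the film is required only for the asymptomatic form.

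Two further sentences could bear on the denominator. Section 4.5 says: "All analysis will be carried at a tooth level, where each tooth will be accounted for as an individual case". Section 6.2 says: "Intention to treat analysis will also be carried out".

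**The concern.** A symptomatic tooth without a radiolucency has apical periodontitis at baseline but nothing on the film to resolve. It falls under the research question, yet the only yes/no rule does not fit it. Three scorings are possible: healed (no radiolucency at 18 months), not healed (nothing resolved), or left out. A new lesion in such a tooth would not be a failure under the resolution rule, and the symptoms recorded at review are not part of that rule.

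Primary aim 1 is a frequency, so the choice could move it. If these teeth stay in the denominator with one fixed score in both arms, they add no contrast and pull the arms together. Section 8.0 says the results could show that antibiotics are not required, so a diluted difference could be taken as support for that.

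**Working it through.** **1. The plan's own figure.** Section 3.5 gives 30 teeth per group from a difference of 1.5, SD 2, two-sided 0.05 and 80% power. By the normal approximation, n = 2 × (1.96 + 0.842)² × (2/1.5)² = 2 × 7.85 × 1.778 = 27.9, so 28. The t-test solution is 28.9, so 29. The stated 30 is consistent with its inputs. It is for root length, so no scoring of periapical healing alters it.

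**2. Does any text put lesion-free teeth into the resolution denominator?**

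| Text | What it settles |
|---|---|
| 3.4.2.4 item 2 | Speaks of an existing radiolucency, compared with the pre-operative film. Taken plainly, it covers teeth that had one. |
| 4.5, tooth-level analysis | The unit of analysis. Section 3.4.2.3 explains it: two teeth from one patient count separately. |
| 6.2, intention to treat | Stands in a paragraph on missed recalls and drop-outs. |
| 3.4.2.3, radiographs | Every film is evaluated for periapical status, so a new lesion would be recorded. |
| 3.4.2.4 item 1 | Names the PAI as the periapical score, without a cut-off. |

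None of these forces a lesion-free tooth into the rule.

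**3. What would happen if they were put in.** Let f be their share, equal in both arms, and a and b the resolution rates in teeth with a lesion. Neither is in the protocol. Assume f = 10% to 40%, a = 90%, b = 60%.

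- Scored healed: f + (1 − f)a versus f + (1 − f)b.
- Scored not healed: (1 − f)a versus (1 − f)b.
- The difference is (1 − f)(a − b) in both cases: 0.9 × 30 = 27 points, or 0.6 × 30 = 18 points.
- Left out: a versus b, with 30(1 − f) = 27 to 18 teeth per arm.

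| Scoring | f = 10% | Power | f = 40% | Power |
|---|---|---|---|---|
| Healed | 91% v 64% | 74% | 94% v 76% | 53% |
| Not healed | 81% v 54% | 61% | 54% v 36% | 29% |
| Left out | 90% v 60% | 77% | 90% v 60% | 56% |

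Power is for a two-sided chi-square test at 0.05 by exact binomial enumeration, with 30 teeth per arm in the first two rows. With no lesion-free teeth it is 80%.

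**4. Unequal shares.** The factor (1 − f) holds only if f is the same in both arms. With 15% in the better arm and 25% in the other:

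- Scored healed: (0.15 + 0.85 × 0.90) − (0.25 + 0.75 × 0.60) = 0.915 − 0.700 = 21.5 points.
- Scored not healed: 0.85 × 0.90 − 0.75 × 0.60 = 0.765 − 0.450 = 31.5 points, wider than the true 30.

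**5. Is a 30-point gap a natural case?** In the retrospective series in section 3.5, 85 − 8 = 77 teeth were not lost to follow-up, and 7 of them are reported with periapical pathology. That is 9%, or about 91% without it. Periapical status is not stated for every tooth in the series, and its treatment may differ from the trial's. If 91% pooled healing did hold, the widest gap with equal arms would be about 100% versus 82%, or 18 points. For 90% versus 80%, 10 points becomes 9 to 6, and power is 19% or less under every scoring.

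**The case for a change.** The strongest reply is that two things the protocol itself fixes do not fit together. The eligibility list distinguishes symptomatic teeth, with or without a lesion, from asymptomatic teeth, which must have one. The abscess diagnoses and the inflamed-pulp item state no radiographic requirement either, so there may be other routes in. The research question is about the disease, while the rule is about the film. An unstated denominator could also be chosen after the results are seen.

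Part of this stands. The protocol names no denominator for primary aim 1, the resolution rule does not count a new lesion as a failure, and the statistical analysis plan should settle both before the films are read.

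The rest does not make the protocol wrong. An outcome that applies only to part of the trial population is no contradiction. Restricting it to teeth with a baseline radiolucency is also statistically safe: the film is taken before treatment (3.4.2.3), allocation follows canal debridement (3.2) and assessors are blinded (4.3), so the restriction uses a feature fixed before randomisation. An amendment to that effect would restate the plain reading of item 2. In the illustration it would gain only 3 points of power over scoring these teeth healed (77% against 74%, and 56% against 53%). A dichotomised PAI for all teeth would show new lesions but would not remove the dilution.

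**Conclusion.** No change to the protocol follows. It leaves open a denominator and a PAI cut-off, which a statistical analysis plan commonly supplies and which can be filled sensibly from data already collected: resolution among teeth with a radiolucency on the pre-operative film, and PAI at 18 months for all teeth. The plain reading of the resolution rule already leads to the first.

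The possible harm, 30 points falling to 27 to 18, needs three assumptions together: lesion-free teeth forced into a rule whose wording leaves them out, a share of 10% to 40% that the protocol does not give, and resolution of 90% versus 60%. It disappears if few lesion-free teeth enrol or if they are left out. No stated power is affected.

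### The outcome matching primary aim 1 (periapical healing) is purely radiographic, so a tooth with swelling or an abscess at 18 months but no radiolucency can count as resolved

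*Protocol*

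**What the plan says.** Protocol section 2.0 asks, as research question 1.i, about "Resolution of apical periodontitis". Its first primary aim is "To assess frequency of periapical healing in the two sets of experimental protocols".

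Section 3.3(i) names the corresponding outcome as "Resolution and healing of periapical radiolucency". In section 3.4.2.4, item 1 grades lesion size by the periapical index, and item 2 gives the only yes/no criterion for resolution: "Defined as the complete absence of existing periapical radiolucency as compared with pre-operative radiograph". The later list of evaluated parameters in the same section adds only reduction or resolution of the lesion, which is also read from the film.

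Section 3.4.2.3 states that "The primary purpose of review appointments is to assess healing and continued root development". Its list of clinical review items includes pain, tenderness to percussion and palpation, and "No evidence of labial swelling or abscess, signifying continued presence of infection". The timing is fixed there too: "Final outcome measures will be recorded at the 18th month review".

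**The concern.** The research question is about a disease, while the outcome is about an image. The protocol says that swelling or abscess indicates continuing infection, yet it lets the healing outcome be decided without looking at either sign. The trial compares two disinfection dressings, so residual infection is the kind of failure this outcome should be able to detect.

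If teeth with clinical infection and a clear radiograph occur more often in one arm, the comparison of healing frequencies is biased in that arm's favour. If they occur equally often in both arms, the difference stands but both healing rates are overstated.

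**Working it through.** This is mainly a matter of reading the sections against each other. The arithmetic only gives scale.

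**Step 1: is any measure of periapical healing not radiographic?** Section 3.3(i) refers to the radiolucency. Section 3.4.2.4 item 1 (periapical index) and item 2 (absence of radiolucency) are both read from the radiograph, as is the later parameter on lesion reduction or resolution. None has a clinical component.

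**Step 2: does another section supply the link?** Section 3.4.2.3 lists clinical and radiographic items under one visit purpose but gives no rule for combining them. Section 3.4.2.4 assigns two assessors to clinical and radiographic analysis but defines no clinical criterion of healing for them to apply. Section 4.5 adds nothing on this point.

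**Step 3: apply item 2 to two kinds of tooth.**

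| Tooth at 18 months | Item 2 | Section 3.4.2.3 |
|---|---|---|
| Baseline lesion gone, abscess present | Criterion met | Continuing infection |
| No baseline lesion, no radiolucency, swelling present | No existing lesion to disappear; failure cannot be registered through the swelling | Continuing infection |

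The second row can occur because section 3.4.1 admits symptomatic apical periodontitis whether or not the radiograph shows a lesion.

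**Step 4: compare with the rest of the protocol.** Section 3.4.1 accepts acute and chronic apical abscess as entry diagnoses and treats swelling and abscess as signs of non-vitality. Section 3.4.2.2 uses clinical signs to judge infection at the second treatment visit. Only the healing outcome leaves them out.

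**Step 5: the plan's own figure.** Section 3.5 states 30 per group for a root-length difference of 1.5, SD 2, two-sided alpha 0.05 and 80% power:

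n = 2 × 2² × (1.960 + 0.842)² / 1.5² = 2 × 4 × 7.85 / 2.25 = 27.9, so 28 per group. A t-test calculation gives 28.9, so 29.

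Both are close to the stated 30. The calculation uses root length, so the definition of healing does not enter it.

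**Step 6: scale.** The inputs are 30 teeth per arm (section 3.5) and 10% dropout (section 6.2), so 30 × 0.90 = 27. If k teeth in an arm change from healed to not healed, that arm's frequency falls by k/n:

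| k | n = 30 | n = 27 |
|---|---|---|
| 1 | 3.3 points | 3.7 points |
| 2 | 6.7 points | 7.4 points |
| 3 | 10.0 points | 11.1 points |

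With equal arms, the between-arm difference changes by (k in one arm − k in the other)/n. Equal counts therefore leave it unchanged. The protocol gives no value for k, so the rows are illustrations and not estimates.

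**The case against.** **Item 2 is a rule for reading radiographs.** It sits in a section on radiographic analysis and defines resolution of the lesion, one of eight parameters. No sentence equates it with periapical healing in aim 1. This stands as a limit on wording: a reader might infer that the protocol declares infected teeth healed, and it does not say so. But section 3.3(i) names the outcome by radiolucency and no other criterion is offered, so such a tooth can count as resolved.

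**The clinical signs are not lost.** Section 3.4.2.3 lists them among the outcomes assessed at review, and the assessors' task covers clinical analysis. This also stands. An abscess at 18 months would be recorded, and a combined analysis would remain possible. What is missing is its bearing on the healing outcome.

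**A combining rule belongs in the statistical analysis plan.** This would hold if the protocol were silent. It has instead fixed a radiographic outcome that conflicts with its own statement about infection and fits poorly with teeth it admits without a lesion.

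**Pain and tenderness.** A reader might treat every clinical item as a sign of infection. The protocol says this only of swelling or abscess, so it does not support making pain or tenderness an automatic failure.

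**Size.** A reader might assume that 3–10% of teeth have clinical signs without radiolucency, which is about 2 to 6 of 60, and set that against the failures expected from the series in section 3.5 (7 of 85 − 8 = 77 followed teeth, 9.1%). The first figure has no source in the protocol. The seven failures are described as having open apices and signs of periapical pathology, and nothing shows that any was invisible on a radiograph. The comparison should not be used.

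**Conclusion.** The point holds as an inconsistency in how an outcome is defined. The outcome matching primary aim 1 and its only yes/no criterion are radiographic, and nothing ties them to signs that the protocol itself reads as continuing infection. The criterion can therefore pass a tooth that has not met research question 1.i. It also cannot register clinical failure in eligible teeth without a baseline lesion.

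This rests on linking aim 1 to item 2 through section 3.3(i), which is an inference, though the only one the text offers. The number of affected teeth is unknown. Each would move an arm's healing frequency by 3.3 points at 30 teeth or 3.7 at 27. Bias between arms arises only if such teeth are unevenly distributed, and the protocol has no data on that. Neither the root-length endpoint nor the sample size is affected. The definition should be corrected, but the point does not call the design into question.

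**What to change.** In section 3.3(i), define periapical healing at 18 months as absence of periapical radiolucency **and** no swelling or abscess as already recorded under section 3.4.2.3. Refer to absence of any periapical radiolucency, not of the existing one, so that teeth without a baseline lesion can also be classified. Keep item 2 of section 3.4.2.4 as the radiographic component and report the radiograph-only result as a supporting analysis. Tenderness and pain may be added to the definition in a sensitivity analysis. Settle the rule before outcomes are examined by arm.

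The cost is one definition. No new visit, test or radiograph is needed, and the sample size does not change. The reported healing rate may be slightly lower.
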